9.1.2. Secondary Design - SCRI Design with Post-Vaccination Control Interval

In addition, the SCRI design uses information from cases (ie, individuals who experience a safety event following vaccination) to compare the risk interval following vaccination to post-vaccination non-risk intervals ("post-vaccination control interval") in the same individual. AGAT Only ABRYSVO vaccinated individuals who experience an outcome of interest within the risk or control interval will contribute to the SCRI analysis. As the SCRI design is a within person analysis, it implicitly controls for time fixed confounders. Time varying confounders still need to be controlled for, but with short, defined risk windows the risk of time varying confounding is limited.

To ensure all individuals have the same chance of having a confirmed diagnosis, the SCRI analysis will require individuals to have continuous enrollment in VHA benefits for an additional 30 days following the risk and post-vaccination control interval (eg, a total of 40 days of follow-up comprised of the day 0-3 risk interval [including the day of ABRYSVO vaccination], day 4-10 control interval, and additional 30 days of follow up). Note that a longer control interval of 7 days (ie, day 4-10 corresponding to the day 0-3 risk interval and day 2-8 corresponding to the day 0-1 risk interval) will be used to increase power of detecting an association should one truly exist by providing a more statistically stable estimate of the baseline risk while avoiding the confounding impact of time-varying covariates (eg, seasonality, other vaccination, medication use). Since the required post-vaccination follow-up period is short, this requirement is not expected to produce any appreciable selection bias in the analysis.

The SCRI design with a post-vaccination control interval is presented in Figure 1 below.

Figure 1. Example of SCRI Design for Assessment of a Safety Event with a 0-3 Days Risk Interval in the ABRYSVO Cohort*

^{*} Figure is not drawn to scale.

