9.1.1. Primary Design - Internal Comparator Cohort Design (Contemporary Control Design)

To examine atrial fibrillation and supraventricular arrhythmia following ABRYSVO vaccination, days 0-3 will be used to define the risk interval, comprising a length of 4 days (ie, from the day of vaccination through the 3 days that follow, as only the date and not exact timing of vaccination will be known) for the primary analysis. This risk interval was selected based on post-marketing reports indicating atrial fibrillation onset less than one day after ABRYSVO administration, while accounting for a potential delay between the actual event

onset and when individuals seek care. As secondary analyses, days 0-1 comprising a length of 2 days (ie, the day of vaccination and the day following) will be used to define the risk interval, and days 0-30 comprising a length of 31 days (ie, the date of vaccination through the 30 days that follow) will be used to define the risk interval, similar to other studies that evaluated the risk for cardiac events (eg, myocarditis and pericarditis) to assess the safety profile of COVID-19 vaccines. ¹⁰⁻¹⁴ To reduce outcome misclassification, a confirmed case will require a diagnosis of atrial fibrillation (or supraventricular arrythmia) in the risk interval, with a confirmatory diagnosis within the subsequent 30 days for the primary and secondary analyses with different risk interval lengths (see Section 9.3.2).^{8,9}

Multivariable adjusted analyses will be performed comparing individuals who received ABRYSVO to individuals who received another vaccine (eg, influenza vaccine, COVID-19 vaccine, and other pre-specified vaccines such as shingles, hepatitis B listed in Section 9.3.3) at that point in time (+/- 30 days) [ie, contemporary vaccinated controls] in the primary analysis. The ABRYSVO cohort's index date will be defined as the date of vaccination with ABRYSVO. The vaccinated controls' index date will be defined as the date on which the individual received another vaccine that is within 30 days of a corresponding ABRYSVO vaccinee's vaccination date; these individuals can later receive ABRYSVO and enter the vaccination group if all eligibility criteria are met.

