As a secondary analysis, individuals who received ABRYSVO will be compared to individuals not receiving any vaccinations at that point in time but had at least one vaccination record in the year prior to the index date (ie, contemporary unvaccinated controls). The unvaccinated controls will be assigned an index date matched to a corresponding ABRYSVO vaccinee's vaccination date; these individuals can later receive ABRYSVO and enter the vaccination group if all eligibility criteria are met. To address possible selection bias due to health seeking behaviors, the unvaccinated controls will be randomly selected from a population of patients who have regular use of preventive medical care within the VHA system, defined as at least one vaccination record in the year prior to the index date. The index date for the contemporary unvaccinated controls will be selected based on the observed index dates in the vaccinated cohort. If ABRYSVO vaccination is associated with a regular healthcare encounter, the contemporary unvaccinated control will be required to have an encounter within 30 days of the assigned index date, and the date of encounter will be set as the index date to ensure comparability of covariate measurement.

In the primary analysis, the ABRYSVO vaccinated, contemporary vaccinated control, and contemporary unvaccinated control cohorts will be followed for up to 34 days post-index (ie, 0-3 day risk interval plus 30-day diagnosis confirmation window) to assess and confirm the occurrence of atrial fibrillation and supraventricular arrhythmia. In secondary analyses, the cohorts will be followed up to 32 days post-index (ie, 0-1 day risk interval plus 30-day diagnosis confirmation window) and up to 61 days post-index (ie, 0-30 day risk interval plus 30-day diagnosis confirmation window). Individuals will be censored upon the earliest occurrence of disenrollment, death, date of RSV vaccination (for controls who later receive any RSV vaccine only), or end of the risk window. The date of the first atrial fibrillation (or supraventricular arrythmia) case will be considered date of onset.

[figure not shown]

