9.3.2. Outcomes

The study's primary outcome, new onset atrial fibrillation, will be identified by a diagnosis code for atrial fibrillation in any setting during the 0-3 day risk interval (or 0-1 day or 0-30 day risk interval for secondary analysis), or corresponding control interval, followed by a confirmatory diagnosis within 30 days after the initial diagnosis. To be considered an incident case, no diagnosis for atrial fibrillation or other supraventricular arrhythmia should be observed in the 2 years prior to the index date (ie, "clean window," the occurrence-free

baseline period used to define incident outcomes during which individuals enter the study cohort only if the safety event did not occur during this period).^{8,9}

The secondary outcome of the study will be new onset supraventricular arrhythmia, including atrial fibrillation, and will be identified in the same manner as the primary outcome (ie, a diagnosis code for the event in any setting during the risk interval, or control interval, followed by a confirmatory diagnosis within 30 days after the initial diagnosis, and no diagnosis code for atrial fibrillation or other supraventricular arrhythmia in the 2-year clean window).

The study outcomes and operational definitions of the outcome variables based on International Classification of Diseases, Tenth Revision, Clinical Modification (ICD-10-CM) diagnosis codes are outlined in Table 1. ICD-10-CM diagnosis codes occurring in any position (ie, primary or secondary) in OP (including emergency department [ED]) and/or IP settings will be used to identify safety events.

Table 1. Safety events, including outcome algorithms and risk and control intervals

Safety Event	Operational Definition Defined by the presence of any of the following ICD- 10-CM codes (inclusive):	Setting (IP, OP)	Clean Window	Risk Interval (Days)	Post- Vaccination Control Interval for SCRI Design (Days)
Atrial fibrillation (primary outcome) ⁵⁰	 I48.0, Paroxysmal atrial fibrillation I48.19, Other persistent atrial fibrillation I48.20, Chronic atrial fibrillation, unspecified I48.91, Unspecified atrial fibrillation 	IP or OP	2 years	Primary: 0-3 Secondary : 0-1 and 0-30	Primary: 4-10 Secondary: 2-8 and 31- 61

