A conditional Poisson regression model will be used to compare the rates of safety events in the risk interval vs post-vaccination control time period. From this model, we will report rate ratios and 95% CIs that will be interpretated as the relative incidence for the safety event in the risk interval compared to the control interval.

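### In the SCRI, the 0-1 day risk window is set against a full control week with no day-of-week term named, so weekday coding patterns alone could move the rate ratio off 1

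*Protocol*

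**What the plan says.** Protocol 9.1.1 sets the risk windows: "days 0-3 will be used to define the risk interval, comprising a length of 4 days" for the primary analysis and "days 0-1 comprising a length of 2 days" for a secondary one. For the SCRI, 9.1.2 gives the primary window "a longer control interval of 7 days (ie, day 4-10 corresponding to the day 0-3 risk interval". The secondary window also gets a control week of its own: "day 2-8 corresponding to the day 0-1 risk interval". Table 1 repeats these pairings and adds days 0-30 against 31-61.

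Section 9.1.2 accepts that time-varying confounders need control in a within-person analysis, then adds that "with short, defined risk windows the risk of time varying confounding is limited". It says the 7-day control interval avoids such confounding, with seasonality, other vaccination and medication use as examples. Day of week is not mentioned.

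Events are dated by diagnosis: "The date of the first atrial fibrillation (or supraventricular arrythmia) case will be considered date of onset" (9.1.1). Codes "in OP (including emergency department [ED]) and/or IP settings will be used to identify safety events" (9.3.2). The analysis is stated in 9.7.2.3: "A conditional Poisson regression model will be used to compare the rates of safety events in the risk interval vs post-vaccination control time period". No covariate or calendar term is named there.

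**The concern.** A 7-day control interval has the same weekday make-up for every case, whatever the day of vaccination. A 2-day or 4-day window has not: its make-up depends on the weekday on which the vaccine was given. If vaccines are given mostly on working days and AF is coded less often at weekends, as is plausible where outpatient codes count, the short window collects more high-coding days per day of observation than the control week does. The rate ratio then exceeds 1 without any vaccine effect. Shortening the window can enlarge the imbalance, so the rationale in 9.1.2 does not carry over to this confounder.

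The 0-1 day window is the one most exposed. It is also the one nearest to the post-marketing reports cited in 9.1.1, with onset under a day after vaccination. An imbalance of this kind does not shrink as cases accrue, and an observed increase in risk triggers the risk-factor analysis of 9.7.2.5.

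**Working it through.** **The plan's own figures.** The protocol gives no figure for weekday bias. Table 3 supplies the event counts used below, so I checked it first, using the signed-root likelihood-ratio sample-size formula for self-controlled case series with one-sided alpha 0.05 and 80% power. For 2 risk days and 7 control days it gives 193.7 events (RR 1.5) and 61.8 (RR 2), against 197 and 64 in the table. For 4 and 7 days it gives 154.8 and 52.0, against 156 and 53. The vaccinee numbers for age 60 and over follow from the control-interval events: 41 / (0.0339 × 7/365) = 63,064 and 138 / (0.0339 × 7/365) = 212,263, as stated. The table therefore rests on a 4-day primary window, although its note gives 3 days; that note should be reconciled.

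**Inputs.** From the protocol: the window pairs, the dating of events by diagnosis, and the code settings. Assumed, because the protocol gives neither: the distribution of vaccination over the week, and *r*, the weekend daily AF coding rate as a fraction of the weekday rate.

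**Formula.** Let *s* be the average share of risk-window days that fall on weekdays. Under no vaccine effect,

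RR = [s + (1 − s)r] / [(5 + 2r)/7].

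**Weekday shares, vaccination even over Monday-Friday**
- Days 0-1: (2+2+2+2+1)/10 = 0.90
- Days 0-3: (4+4+3+2+2)/20 = 0.75
- Any 7-day control interval: 5/7 = 0.714

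**Rate ratio under no vaccine effect**

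| r | 0-1 vs 2-8 | 0-3 vs 4-10 |
|---|---|---|
| 0 | 0.900/0.714 = 1.26 | 0.750/0.714 = 1.05 |
| 0.5 | 0.950/0.857 = 1.108 | 0.875/0.857 = 1.021 |
| 0.8 | 0.980/0.943 = 1.039 | 0.950/0.943 = 1.008 |
| 1 | 1.00 | 1.00 |

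**Other vaccination patterns (all assumed)**
- 10% at weekends (18% on each weekday, 5% on each weekend day): for days 0-1, s = (0.18×9 + 0.05×1)/2 = 0.835. RR = 1.17 at r = 0 and 1.07 at r = 0.5.
- Even over all seven days: s = 5/7 for every window, so RR = 1.00 for any r.
- Late-week skew (10, 15, 20, 25, 30% Monday to Friday): for days 0-3, s = 2.7/4 = 0.675. RR = 0.945 at r = 0 and 0.977 at r = 0.5. For days 0-1, s = 0.85 and RR = 1.19 and 1.08.
- Early-week skew (25, 25, 20, 15, 15%): for days 0-3, s = 3.2/4 = 0.80. RR = 1.12 and 1.05. For days 0-1, s = 0.925 and RR = 1.295 and 1.12.

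**Effect on the error rate, days 0-1.** This uses a normal approximation, no true effect, and a nominal one-sided 5% test as in the sizing.

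| RR from weekday pattern | 64 events | 197 events |
|---|---|---|
| 1.039 | 6.7% | 8.0% |
| 1.108 | 10% | 16% |
| 1.26 | 22% | 42% |

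**The case against.** The strongest reply has four parts.

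*The SAP may deal with it.* Section 9.7 leaves detailed methods to the SAP, 9.1.2 concedes that time-varying confounders need control, and 9.7.2.3 names a model without excluding covariates. This stands in part: the absence of a weekday term can be said only of the protocol. But the point rests on a stated rationale that gives the SAP's authors no reason to add such a term.

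*The inputs are not in the documents.* This stands. A reader might take 1.1-1.26 as the expected distortion for days 0-1. The documents do not support that: the range needs Monday-Friday vaccination and weekend coding at half the weekday rate or less, and its top end needs no weekend coding at all, which is unlikely when emergency and inpatient codes count. Section 9.7.1 also lists pharmacies and inpatient wards among vaccination settings, and weekend vaccination shrinks the effect. Nor is the distortion the same for every case mix, since *r* depends on the balance of outpatient, emergency and inpatient diagnoses.

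*It touches a secondary window of the secondary design.* This stands. In the primary cohort comparison, vaccinated controls are indexed on their own vaccination date and have the same risk interval, so their windows also start on a vaccination day.

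*Negative control outcomes would show it.* Section 9.7.4.1 applies the methods of 9.7.2, SCRI included, to outcomes such as cataracts. If their coding also falls at weekends, a non-null result could expose the artefact. It would not remove it from the AF estimate.

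**Conclusion.** The point holds for the 0-1 day SCRI analysis, as a modest distortion of conditional size. Under even Monday-Friday vaccination and weekend coding at 0.5-0.8 of the weekday rate, the rate ratio with no vaccine effect is about 1.04-1.11. Under that vaccination pattern 1.26 is the ceiling. It falls to about 1.07 at r = 0.5 with 10% weekend vaccination, and to 1.00 if vaccination is even over the whole week.

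For days 0-3 the effect is small, about 1.01-1.05 under even Monday-Friday vaccination. A reader might infer that this analysis is biased upward by a few percent. The documents do not fix even the sign: an assumed late-week skew takes the ratio below 1.

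The reassurance in 9.1.2 is reasonable for the examples it gives, such as seasonality. It is incomplete because day of week is an exception. This is a worthwhile and cheap improvement to a secondary analysis and does not undermine the primary comparison.

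**What to change.** In 9.7.2.3, split each case's risk and control time into single days and include a weekday/weekend (or day-of-week) term in the conditional Poisson model for the 0-1 and 0-3 day analyses. Report the adjusted rate ratio as the SCRI result. The term can be estimated because each control week contains every day of the week. It removes only the weekday component.

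In 9.1.2, keep the statement about short windows but add that day of week is an exception, and that the model deals with it.

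The cost is a few lines of protocol and SAP text and one model term on dates already held. The downside is slightly wider confidence intervals.

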9.7.1. Baseline Characteristics

Baseline demographics and clinical characteristics for individuals administered ABRYSVO, contemporary vaccinated controls, and contemporary unvaccinated controls will be summarized using descriptive statistics, consisting of the mean, standard deviation (SD), median, and interquartile range [IQR] values for continuous variables and frequency distributions for categorical variables. Standardized differences will be calculated between individuals who received ABRYSVO and contemporary vaccinated controls, and between individuals who received ABRYSVO and contemporary unvaccinated controls. Standardized differences <10% will indicate that the characteristics between recipients of ABRYSVO and the comparator cohort are balanced.

Descriptive statistics will also be used to summarize ABRYSVO characteristics, including calendar year and month of vaccination and care setting of vaccination (eg, OP clinic, pharmacy, IP ward).

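### The SCRI risk window includes the vaccination day and its control window cannot, so AF first coded at the vaccination contact can raise the rate ratio with no vaccine effect; no analysis without day 0 is specified

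*Protocol*

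**What the plan says.** Protocol section 9.1.1 states that "days 0-3 will be used to define the risk interval, comprising a length of 4 days". Day 0 is included "as only the date and not exact timing of vaccination will be known", and the window is supported by post-marketing reports of onset less than one day after the dose. Section 9.1.2 uses the same window for the SCRI, requiring "a total of 40 days of follow-up comprised of the day 0-3 risk interval [including the day of ABRYSVO vaccination], day 4-10 control interval" and 30 further days, and pairs the intervals as "day 4-10 corresponding to the day 0-3 risk interval and day 2-8 corresponding to the day 0-1 risk interval".

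Under section 9.3.2 the outcome is "identified by a diagnosis code for atrial fibrillation in any setting during the 0-3 day risk interval" or in the control interval, with a confirmatory code within 30 days and none in the previous 2 years. The codes accepted are "ICD-10-CM diagnosis codes occurring in any position (ie, primary or secondary) in OP (including emergency department [ED]) and/or IP settings". Section 9.1.1 adds: "The date of the first atrial fibrillation (or supraventricular arrythmia) case will be considered date of onset".

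Section 9.7.1 summarises, for ABRYSVO recipients, "calendar year and month of vaccination and care setting of vaccination (eg, OP clinic, pharmacy, IP ward"). Sections 9.1.1 and 9.2.1 treat a healthcare encounter at vaccination as conditional. They use it only to require a matching encounter for unvaccinated controls.

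The protocol gives no rule for a code entered at the vaccination contact or during an admission in which the dose was given. It specifies no SCRI analysis without day 0.

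**The concern.** A self-controlled design removes confounders that are fixed within a person. A contact with the health system on one particular day is not fixed. Some risk windows contain a coded encounter because the dose was given there, and the control window has no counterpart. AF noticed at that visit, or already known and listed as a secondary diagnosis, is counted as new onset on day 0 even if it preceded the injection.

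The 2-year clean window does not close this route. Section 9.4 says the VHA warehouse lacks care received outside VHA facilities. Section 9.3.3 treats AF before the baseline period as a covariate, not an exclusion. AF managed elsewhere, or last coded more than 2 years earlier, can therefore reappear as an incident case.

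Section 9.9 defends a post-vaccination control interval on the ground that people are more vigilant after a vaccine than before it. That does not address the vaccination visit itself. Section 9.1.2 relies on short windows to limit time-varying confounding, but the shorter the window, the more a one-day spike weighs in it.

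At stake is a false excess in the plan's within-person comparison. It could also start the risk-factor analysis of section 9.7.2.5.

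**Working it through.** **Inputs from the protocol.** Risk windows of 4 days (0-3) and 2 days (0-1), control windows of 7 days, a background rate of 33.9 per 1,000 person-years at age 60 and over, one-sided alpha 0.05 and 80% power (sections 9.1.2 and 9.5.1). The daily rate is λ = 0.0339/365 = 9.288 × 10⁻⁵.

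**Reproducing Table 3 (60 and over, days 0-3).** The method is the signed-root likelihood-ratio formula for self-controlled case series. For rate ratio ρ, let r = 4/11, d = ρr + 1 − r, A = 2[(ρr/d) ln ρ − ln d] and B = (ln ρ)² ρr(1−r)/(A d²). The number of events is (z₀.₉₅ + z₀.₈₀ √B)²/A.
- RR 2: 52.0, so 53 events (stated 53).
- RR 1.5: 154.8, so 155 (stated 156).
- Stated control events 25 and 84, divided by 7λ = 6.501 × 10⁻⁴, give N = 38,453 and 129,204, as stated.

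The figures fit a 4-day risk window. The note under Table 3 says 3 days, which would give 166 events at RR 1.5. That is a separate matter, and so is the difference between 40 days of follow-up in section 9.1.2 and 41 in section 9.7.2.3.

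**Bias with no true effect.** Assume a constant daily coding rate except on day 0, where it is k times an ordinary day. Apparent RR is (3+k)/4 for days 0-3, (1+k)/2 for days 0-1 and (30+k)/31 for days 0-30. k is an assumption.

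| k | days 0-3 | days 0-1 | days 0-30 |
|---|---|---|---|
| 1 | 1.00 | 1.00 | 1.00 |
| 2 | 1.25 | 1.50 | 1.03 |
| 3 | 1.50 | 2.00 | 1.06 |
| 5 | 2.00 | 3.00 | 1.13 |

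**What this means in counts.** For days 0-3, an apparent RR of 2 needs k = 5. That is 4λ × 100,000 = 37 extra day-0 codes per 100,000 vaccinees aged 60 and over. An apparent RR of 1.5 needs k = 3, or 2λ × 100,000 = 19.

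**False-positive rate.** 200,000 Poisson simulations per cell, days 0-3 versus 4-10, true RR 1, one-sided 0.05:

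| k | N = 38,453 | N = 129,204 |
|---|---|---|
| 1 | 5% | 5% |
| 2 | 18% | 37% |
| 3 | 39% | 80% |
| 5 | 80% | >99% |

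A larger sample makes the false signal more certain.

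**What k might be.** Suppose a share f of first AF codes arises only at contacts made for another reason, such contacts otherwise occur every D days, and a share p of doses is given at a coded encounter. Then k = 1 + p·f·(D−1). With p = 1 and D = 30, the days 0-3 RR is 1.36, 1.73 and 2.09 at f = 5%, 10% and 15%. A smaller p shrinks the excess over 1 in proportion. None of p, f or D is in the protocol.

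**Without day 0.** Under this model days 1-3 versus 4-10, and day 1 versus 2-8, return RR 1.0 when there is no effect. For RR 2 at age 60 and over, the same formula gives:
- Days 1-3 (r = 3/10): 55 events and N = 55/[λ(2×3+7)], about 45,600 (Table 3 for days 0-3: 53 and 38,453).
- Day 1 (r = 1/8): 90 events and N = 90/[λ(2×1+7)], about 107,700 (Table 3 for days 0-1: 64 and 63,064).

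**The case against.** **Stronger readings that the protocol does not support.** A reader might infer that every case is at a contact where AF can be coded. It does not say so: the encounter is conditional in sections 9.1.1 and 9.2.1, and pharmacy is a listed setting in 9.7.1. A reader might also infer a rate ratio near 2 as the expected result. That needs day-0 coding about 5 times an ordinary day, and nothing in the protocol supplies that. Nor can one say that AF found during an admission falls on day 0. Section 9.4 lists both admission and discharge dates but does not say which one dates the code.

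**Planned safeguards.** Section 9.7.4.1 applies negative control outcomes by the methods of 9.7.2, which include the SCRI, and these could expose visit-day coding. The 30-day confirmation screens out isolated codes. Chart review covers up to 100 cases per report, and its case listing shows days since vaccination. These count, but none removes the artefact. Established AF is readily coded again within 30 days. Section 9.7.2.4 uses review to estimate positive predictive value, states no test of whether onset preceded the dose, and allows review to be waived for the final report.

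**Other limits.** People who postpone vaccination when acutely ill would push the bias the other way. The SCRI is secondary. In the primary comparison vaccinated controls are indexed on their own vaccination date, so both arms have a day-0 vaccination contact. Section 9.7.4 leaves further sensitivity analyses to the SAP, and the covariate list in 9.3.3 is open.

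What stands is the asymmetry in the windows that the protocol fixes, and its direction where doses are given at coded encounters.

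**Conclusion.** The concern holds for the SCRI, with a conditional size. With no vaccine effect, k between 2 and 5 gives an apparent rate ratio of 1.25 to 2.0 for days 0-3 and 1.5 to 3.0 for days 0-1. The days 0-30 analysis is little affected (1.13 at k = 5). These figures assume a constant coding rate on all days but day 0. The real k depends on the share of doses given at coded encounters and is unknown until the data are seen. The primary vaccinated-control comparison is affected only if vaccination settings differ between the arms.

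A reader might conclude that day-0 codes should be deleted from the main SCRI. The protocol does not support that: it chose day 0 because of reports of onset within a day, and deletion could hide a real signal. The defensible conclusion is that the day-0 contribution must be separable, and its reading settled in advance.

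**What to change.** 1. Keep the days 0-3 and 0-1 SCRI analyses as planned.
2. Pre-specify beside them days 1-3 versus 4-10, and day 1 versus 2-8.
3. Report day-0 events separately by care setting, and flag codes that come from the vaccination encounter or from an admission already in progress.
4. State in advance that an excess confined to day 0 will not be read as a vaccine effect unless records or chart review place onset after the dose.
5. Record care setting of vaccination for vaccinated controls as well, and consider it for the propensity score.

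The cost is protocol or SAP wording and a few extra outputs, largely from data the study already plans to extract. The added analyses lose true day-0 onsets and some precision. For RR 2 at age 60 and over, days 1-3 need about 45,600 vaccinees against 38,453, and day 1 alone about 107,700 against 63,064. The day-0 events remain in the planned results.

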3.0	23	6	2,084	
Individuals 18	3-59 years of age	1		
Days 0-3 risk i	interval			
1.2	787	467	5,500,485	
1.5	156	84	989,381	
2.0	53	25	294,458	
3.0	22	9	106,005	
Days 0-1 risk i	interval	1		
1.2	1,025	764	8,998,651	
1.5	197	138	1,625,411	
2.0	64	41	482,912	
3.0	24	13	153,118	
Days 0-30 risk	Days 0-30 risk interval			
1.2	747	340	904,273	
1.5	153	62	164,897	
2.0	54	18	47,873	
3.0	23	6	15,958	

Abbreviations: RR, risk ratio.

Notes:

Sample size calculations for the SCRI design were performed according to the method by Musonda et al.⁶⁷ The calculations are based on assuming one-sided α =0.05, a power of 80%, and the following scenarios: (1) a risk interval of 3 days and a control interval of 7 days (primary), (2) a risk interval of 2 days and a control interval of 7 days (secondary), (3) a risk interval of 31 days and a control interval of 31 days (secondary).

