9.7.2.2. Comparison with Contemporary Controls

Average treatment effect among the treated (ATT) weighting will be used to ensure baseline comparability between the ABRYSVO vaccinated cohort vs. contemporary vaccinated control cohort and between the ABRYSVO vaccinated cohort vs. contemporary unvaccinated control cohort. ATT weighting creates a "pseudo-population" in which the distribution of covariates is, on average, the same in each cohort. ⁶⁸ Specifically, ATT weights will be calculated to allow for estimation of the average treatment effect among individuals receiving ABRYSVO.⁶⁹ This approach will be taken to ensure that inference from the analysis will be applicable to this population. Individuals receiving ABRYSVO will receive an ATT weight of one. Individuals not receiving ABRYSVO will receive an ATT weight equal to the odds of receiving ABRYSVO conditional on their demographic and clinical characteristics as of the index date, which will be calculated based on the propensity score (PS). The PS is defined as an individual's probability of receiving ABRYSVO, conditional on observed baseline covariates, and will be calculated using a logistic regression model. The logistic regression model will include the cohort variable (ie, ABRYSVO vs. vaccinated or unvaccinated control) as the dependent variable, and the independent variables will include variables deemed clinically important and baseline covariates that have standardized differences ≥10% between the two cohorts. Specifically, ATT weights will be PS/(1-PS) for individuals with no record of ABRYSVO. The distribution of weights will be examined to assess extreme values, and truncation will be considered if necessary.

Weighted Cox regression with robust standard errors to account for within-subject correlation will be conducted to compare the risk of safety events between cohorts. Hazard ratios and corresponding 95% CIs will be summarized.

9.7.2.3. SCRI Design using the Conditional Poisson Regression for Comparison to Post-vaccination Control Intervals

SCRI design with post-vaccination control time period will include cases (ie, individuals vaccinated with ABRYSVO who experience safety events following vaccination) who have at least 41 days (or 38 days or 91 days for secondary analysis) of enrollment post-index to compare the incidence of safety events occurring in the risk interval following vaccination with the incidence of safety events occurring during the post-vaccination control interval.

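### The control interval for the 0-1 day SCRI analysis (days 2-8) includes days 2-3, which the primary window treats as risk time; the rate ratio is diluted if diagnoses are in excess on those days.

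*Protocol*

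**What the plan says.** Section 9.1.1 defines the primary window: "days 0-3 will be used to define the risk interval, comprising a length of 4 days". It cites post-marketing reports of onset less than one day after vaccination and extends the window "while accounting for a potential delay between the actual event" and the seeking of care. The short secondary window is "days 0-1 comprising a length of 2 days".

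Section 9.1.2 describes SCRI control time as post-vaccination non-risk time and then pairs the intervals: "day 4-10 corresponding to the day 0-3 risk interval and day 2-8 corresponding to the day 0-1 risk interval". Table 1 gives the same pairs and adds days 31-61 as control for the 0-30 day window. The outcome definition in the abstract lists all three risk windows but names only days 4-10 as control.

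Required follow-up for the primary SCRI is "a total of 40 days of follow-up" in Section 9.1.2, which says that this includes the day of vaccination. Section 9.7.2.3 requires "at least 41 days (or 38 days or 91 days for secondary analysis) of enrollment post-index". The Table 3 note describes "a risk interval of 3 days and a control interval of 7 days (primary", whereas Section 9.1.1 and the sample size text in Section 9.5.1 use 4 days.

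**The concern.** Outcomes are dated by diagnosis code, and Section 9.1.1 takes the date of the first diagnosis as onset. An event that begins within a day of vaccination but is coded on day 2 or 3 counts as a risk-window case in the primary SCRI. In the 0-1 SCRI the same event counts as a control-window case. If such events occur, they raise the control rate and pull the 0-1 rate ratio towards 1. In a safety study that is the direction that hides a signal.

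The disagreeing enrolment figures matter because they are an eligibility rule that has to be programmed. The wrong interval length in the Table 3 note leaves a reader unsure which design the sample sizes describe.

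**Working it through.** **Inputs.** One-sided alpha 0.05, power 80%, 33.9 events per 1,000 person-years at age 60 and over, 2 risk days and 7 control days (Section 9.5.1, Table 3 and its note). Stated result for a rate ratio (RR) of 2: 64 events, 41 of them in the control interval, 63,064 vaccinees.

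**Reproducing the plan's figure.** With r = 2/9 and p1 = RR·r/(RR·r + 1 − r) = 4/11 = 0.3636, the arcsine form is

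n = (1.645 + 0.842)² / {4·[asin√p1 − asin√r]²} = 6.18 / {4·(0.6473 − 0.4909)²} = 63.2, so 64 events.

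Control events: 64 × 7/11 = 40.7, so 41. Vaccinees: 41 / (0.0339 × 7/365) = 63,064. This matches Table 3.

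**Dilution.** Let days 2-3 carry a share q of the day 0-1 excess. The mean rate over control days 2-8, relative to background, is [2·(1 + q(RR − 1)) + 5]/7, so the analysis estimates

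RR_est = 7·RR / [2·(1 + q(RR − 1)) + 5].

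**Power at 63,064 vaccinees, true RR 2.** Background events per day are 63,064 × 0.0339/365 = 5.86. The risk window yields 2 × 2 × 5.86 = 23.4 events. The control window yields 5.86 × [2(1 + q) + 5]. With n the total and p the risk-window share, power = Φ(2√n·[asin√p − asin√(2/9)] − 1.645).

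| q (assumed) | Control events | Total | p | RR estimated | Power |
|---|---|---|---|---|---|
| 0 | 41.0 | 64.4 | 0.364 | 2.00 | 81% |
| 0.25 | 43.9 | 67.4 | 0.348 | 1.87 | 74% |
| 0.50 | 46.9 | 70.3 | 0.333 | 1.75 | 67% |
| 1 | 52.7 | 76.1 | 0.308 | 1.56 | 52% |

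Simulated Poisson counts with a signed-root likelihood-ratio test give the same powers to the nearest percentage point. With q = 1, a true RR of 1.5 is estimated as 1.31 and a true RR of 3 as 1.91.

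**Control days 4-10 instead.** The ratio stays 2:7, so the 64 events, 41 control events and 63,064 vaccinees stand. The estimate is 2.00 for every q above, provided the excess ends by day 3.

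**Enrolment days** (last control day plus 30):

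| Window pair | Day 0 counted | Day 0 not counted | Section 9.7.2.3 |
|---|---|---|---|
| 0-3 / 4-10 | 41 | 40 | 41 |
| 0-1 / 2-8 | 39 | 38 | 38 |
| 0-30 / 31-61 | 92 | 91 | 91 |

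Section 9.7.2.3 mixes the two conventions. Section 9.1.2 says 40 while stating that day 0 is included, but 4 + 7 + 30 = 41. The cohort design counts day 0: 4 + 30 = 34.

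**Table 3 note.** For the 0-3 window the arcsine form with 4 risk days gives 787, 156, 53 and 22 events, exactly as tabulated. With 3 days it gives 856, 168, 56 and 22. The control split agrees: 53 × 7/15 = 24.7 (tabulated 25) with 4 days, against 53 × 7/13 = 28.5 with 3.

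**The case against.** The strongest reply is that the 0-1 window is a separate hypothesis under which days 2-8 are genuinely unexposed, and that nested windows of different length are bound to overlap. Section 9.1.1 reports onset in under a day and mentions only a potential delay, without giving its size. A delay tail would normally fall off, so an excess as high on days 2-3 as on days 0-1 is the extreme case. All of this stands. A reader might infer that the 0-1 rate ratio is biased as a matter of fact, but the documents support only a conditional statement.

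A reader might also extend the argument: control days 4-10 lie inside the 0-30 day risk window, so the primary SCRI would show nothing if risk lasted beyond day 10. That does not follow. The ratio is 1.0 only if the excess is equally high on days 0-3 and 4-10. With RR 3 on days 0-3 and 1.5 on days 4-10, for example, it is 3/1.5 = 2.0. The plan already pairs days 0-30 with days 31-61, and its primary cohort design tests all three windows against other people, where this overlap cannot arise. Section 9.1.2 also gives a reason for a near control interval, namely time-varying factors such as seasonality, other vaccination and medication use.

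Finally, the enrolment and note errors are clerical. That is fair: they move no tabulated number.

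What remains is that the plan's own delay rationale names days 2-3 as days on which vaccine-related diagnoses may appear, and the 0-1 SCRI counts them as non-risk time.

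**Conclusion.** The point holds in conditional form, for one secondary analysis within the secondary design. If days 2-3 carry any of the excess, the 0-1 SCRI understates it. Over an assumed share of 25% to 100%, a true RR of 2 is estimated as 1.87 down to 1.56, and power drops from about 80% to between 74% and 52%. With no excess on days 2-3, or under a true null, there is no bias. The dilution of the estimate does not depend on the background rate, so it applies to both age groups. The 0-3 versus 4-10 comparison is not affected by this overlap.

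The enrolment mismatch and the Table 3 note are real but minor. A reader might take the note to mean that the Table 3 sample sizes are wrong. They are not: they were computed with 4 risk days.

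**What to change.** - **Control interval.** Use days 4-10 as control for the 0-1 window as well as the 0-3 window, in Section 9.1.2 and Table 1. This keeps the 7-day control length and the tabulated sample sizes. Counting day 0, required enrolment for the 0-1 analysis rises from 39 to 41 days.
- **Enrolment rule.** State one convention for day 0 and apply it in Sections 9.1.2 and 9.7.2.3. Counting day 0, as the cohort design does, gives 41 days for both short windows and 92 for the 0-30 window.
- **Abstract.** Align the control intervals named in the outcome definition with Table 1.
- **Table 3 note.** Change the primary risk interval from 3 to 4 days; no figure in the table changes.
- **Optional.** A sensitivity comparison of days 0-3 with days 31-61 would address longer-lasting risk, but is more open to calendar-time change.

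The cost is protocol and SAP wording plus the two extra enrolment days.
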